About right	78%
Too much	0%
Frequency of calls at end of study (%)	
Too little	43%
About right	57%
Too much	0%
Recommend to others (%)	
Yes	96%

Fig. 7. Qualitative feedback of health coaching

based
Health that
A

Randomized Study:

Participants will be randomly assigned in equal proportion to one of two treatments: home PR with health coaching or the attention waitlist control (Fig. 9). Participants randomly assigned to the intervention will receive three months of home PR followed by six months of usual care.

Participants randomly assigned to the active control group will receive three months of usual care plus educational materials and non-coaching calls (matching the number of contacts in the intervention group), followed by three months of home PR plus health coaching and three months of usual care.

Phase 2: Participants randomized to intervention will not change; three months of home PR followed by six months of usual care. Participants enrolled in the active control group will follow the scheme listed above; 3 months of usual care followed by three months of home PR and three months of usual care. During the control wait period they will receive a pamphlet of 12 Healthy Habits during the enrollment period as well as two letters during the control period. The letters will remind them to review the 12 Healthy Habits and will remind them that the exercise portion of the study will start soon.

Phase 3: Forty Mayo participants who have completed the intervention (the 12 weeks of home-based pulmonary rehab with health coaching) will be randomly selected to complete a qualitative interview to explore areas related to the intervention, quality of life and symptom severity. The purpose of the qualitative interview is to take an in-depth look at the appropriateness of the intervention as a potential method of treatment as well as examining the impact on the participant as a whole. Mayo Clinic participants who have completed the intervention portion of the study will be contacted via the telephone to inquire about their interest in participating in the interview. If interested, oral consent will be conducted. A mutually agreed upon time and date for the interview will be confirmed. (A phone script will be used.) The participants will receive \$40 for consideration of their time.

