The interviews will be recorded for subsequent transcription of the interactions. The transcribed interviews will be examined for common themes. Each interview will vary between 20 and 30 minutes and will be performed by a member of the Mindful Breathing Laboratory who is trained in Motivational Interviewing and Qualitative Interviewing. Additional members from the Lab will assist in the transcription of the interviews as well as theme identification. Data collection and analysis will be overseen by [name]. (A guided interview script will be used.)

In addition, the five Mayo Clinic staff who served as health coaches on the study will also be offered the opportunity to be interviewed to learn their experiences in the program. The interviews will be conducted by Qualitative Expert, [name], either in a private space or by phone call. The interview will be recorded so that it can later be transcribed and analyzed. An email inviting the health coach to participate will be sent to the health coach. The health coach will be orally consented and will have the option to opt out.

[figure not shown]

Fig. 9. Randomized study design.

Questionnaires:

Physical QOL will be assessed by the CRQ (Aim 1), SM abilities, self-efficacy (Aim 2), and daily PA and self-efficacy for exercise (Aim 3). These QOL components will be measured at baseline, three, six, and nine months after randomization in both groups. Qualitative analysis (Aim 4) will occur after the intervention in order to further understand the intervention's acceptability and to help interpret the comparative effectiveness findings from Aims 1-3.

Additional QOL questionnaires will include the Interpersonal Support Evaluation List (ISEL-12), the Meaning of Life Questionnaire (MLQ6), and the Longitudinal Analogue Self-Assessment (LASA6). Recent research has indicated that social support and sense of meaning of life are important indicators in the perception of quality of life. The added questionnaires will better measure these important factors.

Study Sites:

The clinical study sites include (1) Mayo Clinic—Rochester, Rochester, MN, (2) Mayo Clinic-Jacksonville, Jacksonville, FL, and (3) HealthPartners® Specialty Center-Regions Hospital, St. Paul, MN. The engineer site is Minnesota HealthSolutions, Maple Grove, MN. These study partners have collaborated for the past five years.

Recruitment

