While participant monitoring does not occur in real time, any significant physiologic abnormality measured during rehabilitation and transmitted to the server (O_2 saturation less than 80% or heart rate >140 or <40 beats per minute) prompts a message to the coach to call the participant to investigate the event. The PI also is alerted within 24 hours by text message if a physiologic abnormality is measured to ensure the appropriate response. In 5R44HL114162-03 Home-Based Health Management of COPD Patients, the remote rehabilitation and health coaching systems have been pilot tested together and found feasible, accurate, and acceptable to participants.

Attention Waitlist Control Group Procedure

Our experience with behavioral studies has shown that retention in a pure control arm is very poor when the active intervention seems intuitively very useful to participants. A waitlist randomized attention control design not only permits each participant to receive an active intervention if assigned to control initially but also maximizes retention and helps fulfill immediate expectations.

During the control group period, participants receive a educational materials on healthy habits for physical activity based on the 12 Habits of Highly Healthy People featured by Mayo Clinic. The control group will also receive two letters aimed at

acknowledging the materials. National Institute of We plan to control for a likely Hawthorne effect that can be observed in the control group as participants may receive more attention than normal. Hence, the difference observed in the control group over time will be deducted from the effects observed in the intervention group when interpreting the results of the study as part of our analysis. The control group then receives the active intervention at month four after being randomized and upon completion of the active control period and the three month measures.

Questionnaires

Questionnaires pertaining to quality of life are administered in the project. The questionnaires are reviewed and entered into REDCap in a timely basis. If a participant indicates a score of 3 or higher on the PHQ 9, the PI will be notified.

Review of medical records, images, specimens – Category 5

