For the continuous study outcomes, changes from baseline to three months will be compared between the study arms using two-sample, two-sided t-tests with 5% type I error rates. Changes in QOL and number of steps will be compared between the two treatment sequences using two-sample two-sided t-tests. No adjustments will be made for multiple testing. Means, SDs, medians, ranges, and frequency distributions will be reported and plotted over time by study arm. Additional analyses will compare changes from baseline to three months. Linear models will be used to assess the impact of treatment arm on three month outcomes after adjusting for the corresponding baseline measure and other variables related to the outcome (age, degree of breathlessness at baseline using the mMRC, and FEV1). Repeated measures mixed models will be used to estimate the intervention effect over the three months of the comparison study. Although there is a crossover element to the study design, crossover analyses will not be used due to the anticipated carryover effect in the intervention arm. Intent-to-treat analyses will also be performed to determine the sensitivity of the results to dropouts and missing values. In the intent-to-treat analyses, if a month three measure is missing for any reason, it will be described as not changing from baseline. Health care utilization (number of ED visits, hospitalizations, and length of stay) between baseline and three months will be treated (analyzed) as both binary (for incidence rates) and continuous (for the number of events). The binary endpoints will all be compared between groups using Fisher's exact test. Logistic regression models will also be fit to look for differences in these outcomes by arm after adjusting for age, mMRC, FEV1, baseline levels of anxiety, depression, and fear, and baseline health care utilization (before starting the study). While significant missing-ness (>5%) in the Aim 1 outcome is not expected, imputation is planned in case it is.

Descriptive summaries of the changes between baseline, three, six, and nine months will be used to assess the effect of the delayed intervention on the control arm and the residual beneficial effect on the intervention arm. These results will be only descriptive and exploratory. No formal hypothesis testing will be done. All data will be stored in REDCap and analyzed using SAS (Cary, NC).

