Missing Values treatment: Initially, Little's test for missing completely at random (MCAR)³⁶ will be used along with Potthoff and colleagues assessment of missing at random (MAR+).³⁷ Contingent on either MCAR or MAR data, imputation will be considered in order to respond to the level of missing-ness and to be able to use the optimal amount of information in our model. In case of participant withdrawal, all available data will be used.

Path analysis: The hypothesized framework will be tested using structural equation modeling (SEM), which allows us to examine multiple dependent variables in one model and concurrently describe multiple paths of direct and indirect effects among the theoretical constructs. We will use two steps in SEM analyses. First, the validity of the measures will be assessed by fitting a measurement model and investigating whether the items are strong indicators of the latent constructs (e.g., self-efficacy and quality of life). The second step involves testing the effect of the predictor variables (e.g., MI training, mastery in PA, social persuasion, physiological and emotional states) on the outcome variables (e.g., self-efficacy, self-management, and physical QOL) with a particular interest in the role self-efficacy has in increasing self-management and physical QOL. In addition to the direct effects of MI training on self-efficacy, self-efficacy on self-management, self-management on physical QOL, mediating effects can be tested, such as the effects of MI training on self-management and physical QOL, or effects of self-efficacy on physical QOL by estimating their indirect effects. The model will be tested using lavaan, the R software package for SEM.³⁸ The model fit will be examined by its model χ^2 , goodness-of-fit index (GFI), and root mean square error of approximation (RMSEA).

Qualitative Analysis (Aim 4): Perceptions of the participants and the interventionist will be captured using qualitative methods. Qualitative inquiry in randomized controlled trials help interpret results and variation in results.³⁹ It can also help ensure that interventions meet stakeholder needs and therefore aid in future transferability of interventions like the proposed system. This is increasingly important as trials move out of controlled settings and into the social context of natural settings,⁴⁰ including participant homes.

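### The analysis assigned to dropout sensitivity is one fixed scenario, zero change for every missing month-3 value, and no planned analysis varies the departure from missing at random (minor)

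*Combined protocol and SAP*

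**What the plan says.** All references are to the combined protocol and SAP.

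- **Analysis Plan, purpose:** "Intent-to-treat analyses will also be performed to determine the sensitivity of the results to dropouts and missing values". The lead analysis is a two-sample t-test on change from baseline to month 3, by implication in those with a month-3 value.
- **Analysis Plan, rule:** "if a month three measure is missing for any reason, it will be described as not changing from baseline".
- **Analysis Plan, other methods:** "Repeated measures mixed models will be used to estimate the intervention effect over the three months of the comparison study". Imputation is also planned should more than 5% of the Aim 1 outcome be missing; no method is given.
- **Missing Values treatment:** after Little's test and an assessment of MAR, "Contingent on either MCAR or MAR data, imputation will be considered". Also, "In case of participant withdrawal, all available data will be used".
- **Questionnaires:** outcomes are "measured at baseline, three, six, and nine months after randomization in both groups", so the comparison window holds only baseline and month 3.
- **Sample Size:** attrition of 5% is expected, with no split by arm.
- **Limitations:** some controls will obtain centre-based rehabilitation. The plan says it will record this and adjust its models for it, and labels that intention-to-treat.

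**The concern.** A sensitivity analysis for dropout should show how bad the missing values would have to be before the conclusion changes. This one tries a single value. In the intervention arm it moves dropouts down by the observed mean change. In the control arm it moves them hardly at all if controls change as little as in the earlier coaching trial (Fig. 6, CRQ Physical Function: -0.01 at 6 months, -0.04 at 12 months). A reader who sees the completer and zero-change tests agree will call the result robust, yet under equal dropout the two agree on significance almost by construction.

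The other methods do not fill the gap. Imputation depends on the data being judged MCAR or MAR. The mixed model assumes MAR and, with only two time points, adds little to the completer analysis.

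The control arm deserves a look. The Attention Waitlist Control Group Procedure reports that "retention in a pure control arm is very poor when the active intervention seems intuitively very useful to participants", and control contact under Phase 2 is "a pamphlet of 12 Healthy Habits during the enrollment period as well as two letters during the control period", against weekly coaching calls in the intervention arm.

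A smaller, separate issue is the Limitations wording. Adjusting for treatment received after randomisation is not, on a plain reading, intention-to-treat.

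**Working it through.** **The plan's own figure.** From a difference of 0.5, SD 1.13, 80% power and two-sided 5%: 2 × (1.96 + 0.84)² × (1.13/0.5)² ≈ 80.2, so 81 per arm and 162 in total (about 163 by the exact t-test). The stated 189 does not follow; it gives about 86% power. The step to enrolment does follow: 189/0.95 = 199, rounded to 200. The mismatch is a separate matter. Only the difference, the SD and 100 per arm are used below.

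**Inputs.** N = 100 per arm and SD s = 1.13 (Sample Size; assumed to apply to change, which the plan does not state). Completer mean changes are mI = 0.50 and mC = 0 (control value close to Fig. 6). Dropout is dI, dC. Only 5% overall is stated; every other rate is an assumption.

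**Formulas.**
- Completers: SE = √[s²/(N(1−dI)) + s²/(N(1−dC))].
- Zero change: estimate = (1−dI)mI − (1−dC)mC; SE = √{Σ over arms of [(1−d)s² + d(1−d)m²]/N}.

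**Worked case, 15% in both arms.** Completers: SE = 1.13√(2/85) = 0.1733, z = 0.50/0.1733 = 2.885. Zero change: estimate 0.85 × 0.50 = 0.425; SE = √[(2 × 0.85 × 1.2769 + 0.1275 × 0.25)/100] = 0.1484; z = 2.864. With complete data the SE would be 1.13√(2/100) = 0.1598.

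| Dropout, intervention/control | Completer z | Zero-change estimate | Zero-change SE | Zero-change z |
|---|---|---|---|---|
| 5%/5% | 3.050 | 0.475 | 0.156 | 3.042 |
| 15%/15% | 2.885 | 0.425 | 0.148 | 2.864 |
| 5%/10% | 3.008 | 0.475 | 0.154 | 3.083 |
| 5%/20% | 2.916 | 0.475 | 0.150 | 3.169 |
| 20%/5% | 2.916 | 0.400 | 0.151 | 2.652 |

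With the Fig. 6 change SDs (0.9 intervention, 1.0 control) the pattern is the same: 3.62 to 3.61 at 5%/5%, 3.43 to 3.39 at 15%/15%, and 3.45 to 3.78 at 5%/20%.

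**Coverage of 0.50 under ignorable dropout, 15%/15%.** Bias/SE = 0.075/0.1484 = 0.505, so coverage ≈ Φ(1.96 − 0.505) − Φ(−1.96 − 0.505) ≈ 92%; simulation gave 92.0%. At 5%/5%, 0.025/0.156 = 0.16, and coverage is about 94.7%.

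**Condition on the rise in z.** At 5%/20% with the effect held at 0.50, zero-change z is 3.16 for a control mean change of -0.01, 3.13 for -0.04, 2.92 (no change) for -0.25, and 2.87 (a fall) for -0.30. The rise needs a control change above about -0.25.

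**What the single point cannot distinguish.** At 5%/20%, with intervention dropouts unchanged, the true effect is 0.95 × 0.5 − 0.20 × 0.5 = 0.375 if missing controls gained 0.5, and 0.95 × 0.5 + 0.20 × 0.5 = 0.575 if they lost 0.5. Zero change gives 0.475 both times.

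**Near the threshold.** With a completer effect of 0.33 at 5%/15%, z goes from 1.956 to 2.066, so the sensitivity analysis is significant when the completer analysis is not.

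**What a shifted imputation shows.** Multiple imputation without covariates, 15%/15%, intervention dropouts shifted by 0, -0.5, -1.0 and -1.5: estimates 0.50, 0.425, 0.35, 0.275; SE 0.173, 0.175, 0.178, 0.182; z about 2.89, 2.43, 1.97, 1.51. The shift of -0.5 is the zero-change scenario with imputation uncertainty carried through: z is 2.43, not 2.86.

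**The case against.** The best defence is that the plan does more than zero-fill. Imputation is triggered above 5% missingness, which is where the rule starts to matter, and mixed models and MCAR/MAR assessments stand beside it. That is right, and nobody should infer that zero change is the only missing-data method planned. None of these methods departs from MAR, however, so the narrower point stands.

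Nor do the documents show that control-heavy loss is to be expected. The remark about poor retention explains why a waitlist was chosen over a pure control. Controls receive the programme once their month-3 measures are done, which gives them a reason to stay. Centre-based rehabilitation is contamination, not missing data. The unequal rates above are illustrations. So is 15%: that Aim 3 needs 170 of the 200 is a power requirement, not an allowance for loss.

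A reader might also infer that the rule is biased in favour of the intervention. The figures do not support that. Null rejection was 4.9–5.2% in simulation under unequal ignorable dropout. When the intervention arm loses more and all dropouts worsen by 0.5 (20%/5%), the truth is 0.325, zero change gives 0.40 and completers 0.50, so the rule corrects part of the error. Under equal dropout the estimate does fall, below the 0.5 minimal important difference if completers show exactly 0.5; only z stands still. Giving one answer whatever happened to missing controls is equally true of the completer and MAR analyses, which is why a grid is needed.

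Finally, at 5%/5% and an effect of 0.50, intervention dropouts would have to be 3.57 points worse than MAR predicts, on a 1–7 scale, before z reached 1.96. Under the planned attrition the grid would change no conclusion. That argument stands, and it limits the severity.

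**Conclusion.** A minor but real weakness. The analysis named for dropout sensitivity is a single non-MAR point, treats filled values as data, and under equal dropout returns nearly the same z as completers (3.050 to 3.042 at 5%; 2.885 to 2.864 at 15%). Its SE at 15% is smaller than complete data would give. If controls drop out more, z rises (2.92 to 3.17 at 5%/20%), provided control mean change is above about -0.25; if the intervention arm drops out more, z falls (2.92 to 2.65 at 20%/5%).

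This rests on SD 1.13 applying to change, a completer effect of 0.50, control change near the Fig. 6 values, and assumed dropout rates. With 200 per arm (the target accrual of 400) the pattern persists: 4.313 to 4.302 at 5%/5%, 4.191 to 4.420 at 5%/15%. At 5% balanced attrition nothing material changes. Confidence is moderate, since the documents give no rates by arm.

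The Limitations wording conflicts with its own label. The lead t-test and the Analysis Plan's covariates do not include centre-based rehabilitation, so the conflict is confined to that sentence.

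**What to change.** 1. Keep the imputation already planned, but specify it: multiple imputation within arm using the baseline value and the FEV1 and mMRC strata, analysed as randomised and not conditional on the MCAR/MAR tests.
2. MAR imputation alone largely reproduces the completer answer, so use it as the anchor for a pre-specified delta-adjusted tipping-point grid. Vary the shift separately by arm and in both directions for controls, for example -1.5 to 0 (intervention) and -0.5 to +1.0 (control) in CRQ points. Report the estimate and interval at each point.
3. Report month-3 missingness by arm.
4. Keep zero change only as a labelled supplementary scenario.
5. In Limitations, state that intention-to-treat analyses do not adjust for centre-based rehabilitation received after randomisation, report its uptake by arm, and label any model that adjusts for it supplementary.

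The cost is SAP wording and modest programming, with no new data. Intervals will be wider: at 15% missing, SE about 0.17 to 0.19 across the grid without covariates, against 0.148 under zero-filling, and somewhat narrower once baseline is in the model. The grid should be fixed before the arms are revealed to the analysts.

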Home Pulmonary Rehabilitation for COPD

NCT03480386

August 23, 2021

General Study Information

Principal Investigator: [name]

Study Title: Home Pulmonary Rehabilitation for COPD

Protocol version number and date: Protocol Version9, August 23, 2021

Research Question and Aims

Hypothesis:

Home-based pulmonary rehabilitation with proper self-management support through health coaching rooted in motivational intervention during pulmonary rehabilitation will improve physical wellbeing, quality of life, increase daily physical activity, and decrease health care utilization for patients with COPD.

Aims, purpose, or objectives:

The ideal system for a home PR program requires straightforward, accurate technology to monitor physiological parameters, patient engagement, and simple exercises to be performed at home, all ensuring participant safety. Feedback is critical: MI-based health coaching, proven effective in COPD,⁶ can translate to higher self-efficacy, subsequently promoting better SM and improved QOL.^{15, 16}

The **aims** of this project:

- Home-based PR will increase PR uptake and adherence, a significant existing gap in COPD care.
- The addition of formal SM support through health coaching during PR may promote behavioral change to prolong the effects of PR on critical COPD health outcomes.
- The home-based PR program may meaningfully engage participants in successful SM and translate into sustained improved physical wellbeing (QOL), increased daily PA, and decreased health care utilization for patients with COPD.
- The proposed home-based PR system using “off-the-shelf” hardware and a previously commercialized software (accomplished through our Small Business Innovation Research Grant, SBIR 5R44HL114162-03) will have a high likelihood of implementation and dissemination once proven effective.

Background:

Role of Pulmonary Rehabilitation in Chronic Obstructive Pulmonary Disease care

International guidelines for managing Chronic Obstructive Pulmonary Disease (COPD), one of the main causes of morbidity and mortality worldwide,¹ suggest that pulmonary rehabilitation (PR) programs and self-management support (SM) are a critical part of treatment. A compelling body of evidence confirms that PR programs deliver improved exercise capacity, reduced breathlessness, and improved health-related quality of life (QOL)² and are associated with fewer acute exacerbations and hospital admissions—the biggest costs burden in health care.^{2, 7}

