Eligible participants (after the screening call) will visit the site for the consenting process. In the clinic visit, all consented participants will receive baseline questionnaires, and information about the system. They will complete the questionnaires during the visit, and take home the ActiGraph™ AM (Fig. 10), to wear for one week. On return of the AM, the study coordinator will randomly assign the participant to intervention or attention waitlist control through a centralized program, Research Electronic Data Capture (REDCap). Randomization will be stratified by whether the participant has poor lung function (forced expiratory volume [FEV1] $<50\%$ predicted) and whether the participant has severe dyspnea (recorded modified Medical Research Council Dyspnea Scale [mMRC] score, 3-4; scale, 0-4); critical factors that can make the study arms unbalanced regarding risk factors. The study coordinator will call the participant and inform him or her of the results of randomization. Intervention participants will be mailed the home-based PR system (pulse oximeter, tablet and Garmin Vivofit™). While blinding participants will not be possible, as most behavioral interventions, the arms will be blinded to the research team in charge of the data entry and statistical analysis and revealed only at study conclusion.

Clinic Visit: Face-to-Face Encounter

The participant will practice the use of the proposed system and the PR routine in the PR lab to ensure understanding and safety; therefore, no home visits are planned. The clinic visit is the best opportunity to evaluate the confidence of the individual in using the system. The study team will provide step-by-step instructions on how to perform the daily home-based PR routine (Fig. 11) and discuss the home environment where PR will take place to define the optimal conditions, particularly safety, for exercise. The participant will be asked to rate their confidence to use the technology presented and their confidence (self-efficacy) to perform the home rehabilitation routine on a scale from 0 (no confidence) to 10 (great confidence). A rating of six or greater will be deemed an acceptable confidence level to participate in the study.

Fig. 10.
ActiGraph™
wGT3X-BT.

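### The adjusted logistic model for the exploratory 3-month utilization outcomes has no safeguard against sparse events; if events are few, a real effect is estimated too far from 1

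*Combined protocol and SAP*

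**What the plan says.** The Analysis Plan covers "Health care utilization (number of ED visits, hospitalizations, and length of stay) between baseline and three months", analysed both as yes/no outcomes and as numbers of events. For the yes/no form, "The binary endpoints will all be compared between groups using Fisher's exact test". Logistic models are fitted as well, comparing arms after "adjusting for age, mMRC, FEV1, baseline levels of anxiety, depression, and fear, and baseline health care utilization".

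The plan gives no utilization event rate, expected number of events, power, sparse-data method or rule for reducing covariates. The 5% level is attached to the continuous outcomes ("two-sample, two-sided t-tests with 5% type I error rates"), and "No adjustments will be made for multiple testing".

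The status of utilization is mixed. The opening hypothesis includes it ("and decrease health care utilization for patients with COPD"). But the account of the earlier coaching trial (Preliminary Data, Project 2) refers to it as an exploratory aim, and the three numbered hypotheses in the Analysis Plan concern quality of life, self-management and physical activity. The statement that no formal testing will be done belongs to the descriptive summaries out to nine months, not to this 3-month comparison.

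**The concern.** Three months is a short window for ED visits and admissions, so the number of participants with an event could be small. Ordinary maximum-likelihood logistic regression with eight predictors and few events has three known problems. When there is a real effect, the estimated log odds ratio lies too far from zero on average. The estimate is imprecise. In some data sets the likelihood has no finite maximum (separation), so no estimate exists.

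If coaching does reduce utilization, the adjusted odds ratio would then tend to overstate the reduction. The plan also does not say what to do if the model fails to converge.

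**Working it through.** **Inputs from the documents.** Sample Size: 200 participants, 100 per arm, 5% attrition. Evaluable: 200 × 0.95 = 190, or 95 per arm. Predictors: arm + age + mMRC + FEV1 + anxiety + depression + fear + baseline utilization = 8, if each takes one degree of freedom; coding mMRC as categories would add more. The plan states no utilization figure that could be reproduced.

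**Assumed input.** Event rate over three months: 5-12%, with 20% as a higher case.

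**Events per predictor.**
- 5%: 190 × 0.05 = 9.5, about 10 events; 10/8 = 1.25.
- 12%: 190 × 0.12 = 22.8, about 23 events; 23/8 = 2.9.
- 20%: 190 × 0.20 = 38 events; 38/8 = 4.75.
- If total N is 400, as under Target accrual, and before attrition: 20 to 48 events at 5-12%, or 2.5 to 6 per predictor.

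**Bias of the planned model.** Simulation with N = 200, 1,500 trials per row, seven independent standard-normal covariates (log odds ratio 0.3 per SD) and true OR 0.50 (log OR -0.693). Firth fits of the same eight predictors used 1,000 trials.

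| Expected events | Mean log OR, ML | exp(mean) | Excess on log scale | Fit failure | Firth, exp(mean) |
|---|---|---|---|---|---|
| 10 | -0.820 | 0.44 | 18% | 4.3% | 0.48 |
| 16 | -0.796 | 0.45 | 15% | 0.3% | 0.51 |
| 23 | -0.759 | 0.47 | 10% | 0.0% | 0.50 |
| 40 | -0.735 | 0.48 | 6% | 0.0% | 0.50 |

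Excess = mean/(-0.693) - 1; for the first row, 0.820/0.693 - 1 = 0.18.

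A second simulation, with N = 190, gave ML means of -0.77 to -0.82 over event rates of 5-20%: exp(-0.82) = 0.44 and exp(-0.77) = 0.46. At the 20% rate the excess was about 10%; other runs at similar event numbers gave 6-8%, so that figure depends on the covariates assumed. In the same simulation, Firth on all eight predictors gave -0.67 to -0.71 (OR 0.51 to 0.49), with root mean squared error about 10-19% below ML at every rate tested.

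With true OR 1 and 10-23 events, the median ML estimate was 1.00-1.02 and the test rejected in 2.3-5.3% of trials, so there is no material bias at the null.

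**Is it the penalty or the number of covariates?** A run that separated the two gave these root mean squared errors:

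| Event rate | ML, 8 predictors | Firth, 8 | Firth, 4 |
|---|---|---|---|
| 5% | 1.06 | 0.84 | 0.82 |
| 8% | 0.74 | 0.66 | 0.65 |
| 12% | 0.66 | 0.58 | 0.55 |

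Nearly all the gain comes from the penalty.

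**Fisher's test.** True size at common rate p is the sum over all tables (a, b) of Bin(a; n, p) × Bin(b; n, p), counting tables with Fisher p ≤ 0.05 (a level assumed here, since the plan states none for this test).

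| Per arm | p = 5% | p = 10% | p = 20% |
|---|---|---|---|
| 95 | 2.0% | 2.8% | 3.4% |
| 100 | 2.1% | 2.9% | 3.3% |
| 200 | 2.9% | 3.4% | 3.7% |

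Power, Fisher then Boschloo:
- 95 per arm: 15% vs 5%, 56% then 62%; 12% vs 4%, 44% then 50%.
- 100 per arm: 15% vs 5%, 58.6% then 63.0%; 12% vs 4%, 46.5% then 50.2%.
- 200 per arm: the gain is about 1-2 points.

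**The case against.** The strongest reply is that the event count is not in the documents. That stands: every size above is conditional on the assumed rates. A reader might infer that the trial will see 10-23 events; nothing in the plan supports that as fact. Total N is also unsettled (200 under Sample Size, 400 under Target accrual), and the larger figure would ease the sparsity.

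The endpoint is exploratory, no sample size rests on it, and the logistic model is an addition to Fisher's test. That also stands, and it limits the severity.

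Several stronger readings do not hold:

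- *Fisher's test is an error.* It keeps type I error below 5%. Its conservatism costs some power, and no 5% level is stated for it. Replacing it is a preference.
- *The odds ratio is inflated.* The bias is away from 1, so a protective odds ratio becomes smaller. It is not material at the null.
- *The analysis ignores the stratification.* Fisher's test does, but "Randomization will be stratified by whether the participant has poor lung function" and by severe dyspnea, and FEV1 and mMRC are both in the logistic model.
- *Anxiety, depression and fear must be dropped.* Under Firth this adds little. With stronger covariates (0.5 per SD), a four-predictor model gave -0.60 to -0.63, because it estimates a different, less adjusted odds ratio. It is a trade-off, not a correction.
- *Anxiety and fear have no instrument.* The readable text names none. But citation numbers jump from 25 in the intervention description to 34 in the Analysis Plan, while the reference list between them includes questionnaire sources. A measures section may simply not be reproduced.

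**Conclusion.** The point holds in a limited form and is minor. The plan commits to an ordinary eight-predictor logistic model without stating how many events it expects. If 5-12% of about 190 participants have an event, a true OR of 0.50 is reported on average (log scale) as about 0.44-0.46, with no usable fit in about 4% of trials at the 5% rate and under 1% at 8-12%. At 20% the log-scale bias is smaller but still about 10%. These figures rest on assumed event rates, a true OR of 0.50 and moderate covariate effects. The conclusion on the primary quality-of-life outcome is not affected.

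**What to change.** In the Analysis Plan, state that logistic models for the binary utilization outcomes will be fitted by Firth's penalised likelihood with profile-likelihood confidence intervals. Keep arm and the seven planned covariates, including FEV1 and mMRC, which carry the stratification factors. Give the assumed event rate, and report the number of participants with an event beside each estimate. This uses the same data and standard software; the cost is SAP wording.

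Optional: use Boschloo's exact test in place of Fisher's for the unadjusted comparison. It holds size at or below 5% and adds about 4-6 points of power at 95-100 per arm, or 1-2 points at 200 per arm. Leaving Fisher's test in place is also acceptable.
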